6.6.2 Principles of management for immune-related adverse events

In overall principle, according to the severity of adverse reaction, interruption of SHR-1210 is taken as the main measure, resumption of SHR-1210 can be considered when the severity of adverse event has recovered to Grade 1 or below, and SHR-1210 should be discontinued permanently when serious Grade 3 or life-threatening Grade 4 adverse events occur.

Management of immune-related adverse events should base on the medical practice of the study site and the guidelines. The following provides the recommendations on management of immune-related adverse events (see Table 5), for reference. Recommended treatment procedures for common immune-related adverse events are detailed in Appendix 4.

Table 5 Recommendations on management of immune-related adverse events

CTCAE Grade	Clinical Treatment*	SHR-1210 Treatment
Grade 1 (Mild)	Close observation; symptomatic and supportive treatment.	Continue
Grade 2 (moderate)	Close monitoring; Symptomatic and supportive treatment; Local or systemic steroids treatment, 0.5–1 mg/kg/day, Prednisone or equivalent drugs.	Interrupted temporarily, resume the medication when adverse reactions ≤ Grade 1; Resuming the medication, except cutaneous and endocrine disorders.
Grade 3 (severe)	Hospitalization is recommended; 1–2 mg/kg/day, prednisone or equivalent drugs (i.v. or p.o.); If failed after steroids treatment for 3–5 days, consider addition of other immunosuppressants; Specialized consultation is recommended.	Interrupted temporarily; dose resumption must comprehensively consider risk/benefit ratio and be decided after discussion.
Grade 4 (life threatening)	Intravenous 1–2 mg/kg Methylprednisolone; If failed after steroids treatment for 3–5 days, consider addition of other immunosuppressants; Specialized consultation is recommended.	Discontinued permanently.

(S. Champiat, O. Lambotte, E. Barreau, et al. Management of immune checkpoint blockade dysimmune toxicities: a collaborative position paper. *Annals of Oncology* 27: 559–574, 2016)

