7.2.2 Criteria for dose delay

The dose should be delayed if the following conditions occur:

- Any \geq Grade 2 treatment-related non-cutaneous AE, except Grade 2 treatment-related fatigue or laboratory abnormalities;
- Any Grade 3 treatment-related cutaneous AE;
- Any Grade 3 treatment-related laboratory abnormalities, except Grade 3 abnormal amylase or lipase unrelated with the symptoms and clinical manifestations of pancreatitis;
- The administration will be delayed if the following AST or ALT abnormalities occurs:
 - AST and ALT at baseline are within normal range, and Grade 2 treatment-related adverse events occur ;
 - AST or ALT at baseline elevates no greater than Grade 1, and Grade 3 treatment-related adverse events occur;
 - AST or ALT at baseline elevates no greater than Grade 2, and treatment-related elevated AST or ALT reaches > 2 times the baseline or either AST or ALT reaches $> 8 \times \text{ULN}$ (whichever is lower).

- The administration needs to be delayed for any AE, laboratory examination abnormalities or complications, as judged by investigators;

Subjects who need delayed dose should be monitored every week, and the frequency of monitoring can be increased when clinically indicated. It is recommended to monitor liver function every three days, until the highest value of AST or ALT starts to decrease. When meeting the criteria for resumption of medication (see Section 7.2.3), the investigational drug can be resumed.

Tumor evaluation still needs to proceed for all the subjects as required in the protocol, regardless of dose delay.

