7.2.4 Criteria for permanent treatment discontinuation

The study medication must be discontinued permanently when the following conditions occur:

- Any Grade 2 treatment-related uveitis, ophthalmodynia, and blurred vision, that has no response to local therapy and is not recovered to Grade 1 after delayed dose; or the above AE requiring systemic therapy.

- Any Grade 3 treatment-related non-cutaneous AE, lasting for > 7 days, except the following:
 - When any Grade 3 treatment-related uveitis, pneumonia, bronchospasm, hypersensitivity, or infusion reaction occurs, the study treatment must be terminated;
 - In case the Grade 3 treatment-related endocrine disorder can be sufficiently controlled only with hormone replacement therapy at physiological dose, the treatment does not need to be terminated;
 - The treatment does not need to be terminated for Grade 3 treatment-related laboratory abnormality, however, the study medication must be terminated for Grade 3 thrombocytopenia > 7 days or related with hemorrhage.
- Hepatotoxicity meeting the following:
 - AST or ALT > 10 times of ULN for over two weeks;
 - ALT or AST > 15 × ULN;
 - TBIL > 8 times of ULN for subjects with elevated TBIL at baseline, > 5 times of ULN for subjects with normal TBIL at baseline;
- Any Grade 4 treatment-related AE or abnormal laboratory examination, except the following:
 - Grade 4 granulocyte decrease lasts less than 7 days;
 - Grade 4 lymphopenia or leukopenia;
 - Isolated Grade 4 elevated amylase or lipase, without symptoms or clinical manifestations of pancreatitis. The sponsor needs to be informed in case of Grade 4 elevated amylase or lipase occurs;
 - Isolated Grade 4 electrolyte imbalance/abnormality without clinical sequela that could be corrected through supplement/appropriate management within 72 hours after occurrence;
 - Grade 4 treatment-related endocrine disorder that can be sufficiently controlled only with hormone replacement therapy at physiological dose, the treatment does not need to be terminated.

- The study treatment must be terminated in case dose delay > 6 weeks is required, except the following:

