9.2.5 Hospitalization

AEs that result in hospitalization or prolonged hospitalization should be considered as SAEs. Any initial hospitalization meets the criteria.

Hospitalization does not include the following situations:

- Rehabilitation facilities
- Nursing homes
- Routine emergency room admissions
- Surgeries at the same day (as outpatient/same day/ambulatory procedures)

Hospitalization or prolongation of hospitalization which are unrelated to the exacerbation of AEs will not be considered as SAEs. For example,

- Admission for treatment of a preexisting condition without the development of new adverse events or worsening of the preexisting condition (e.g., for check of persistent pre-trial laboratory test abnormality);
- Administrative admission (e.g., for yearly physical exam);
- Hospitalization as per the trial protocol during the study (e.g., as required by the protocol);
- Elective admission not associated with the aggravation of adverse events (e.g., elective surgery);
- Predefined treatments or surgical procedures should be documented throughout the study program and/or in the baseline data of individual subject.

- A subject is hospitalized due to only use of blood products.

Diagnostic or therapeutic invasive (e.g., operation) and non-invasive procedures should not be reported as AE, but if the disease condition leading to the operation, it should be reported as long as it conforms to the definition of AE, e.g., acute appendicitis during the AE reporting period should be reported as AE; therefore, the appendectomy should be recorded as the treatment of AE.

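### For Grade 3 immune-related events, the stopping sentence in Protocol 6.6.2 conflicts with its own Table 5, and Table 5 leaves resumption open where 7.2.4 requires a permanent stop

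*Protocol*

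**What the plan says.** Four places in the Protocol tell a site what to do with SHR-1210 after a Grade 3 immune-related event.

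- **6.6.2, opening sentence.** Interruption is the main measure, and resumption may be considered once the event is back to Grade 1 or below. The sentence ends: "SHR-1210 should be discontinued permanently when serious Grade 3 or life-threatening Grade 4 adverse events occur".
- **6.6.2, Table 5, Grade 3 (severe) row.** The clinical column includes "Hospitalization is recommended". The drug column reads "Interrupted temporarily; dose resumption must comprehensively consider risk/benefit ratio and be decided after discussion". Only the Grade 4 (life-threatening) row stops the drug permanently. The table is offered for reference, and 6.6.2 sends the reader on to Annex 4 (called Appendix 4 in the text).
- **7.2.2 and 7.2.3.** Dosing is delayed for treatment-related non-cutaneous events of Grade 2 or higher, with exceptions for fatigue and laboratory findings. It is also delayed for "Any Grade 3 treatment-related cutaneous AE" and for most Grade 3 laboratory abnormalities. In general, dosing may resume at Grade 1 or baseline.
- **7.2.4.** This section is worded as mandatory. It stops treatment permanently for "Any Grade 3 treatment-related non-cutaneous AE, lasting for > 7 days, except the following". Among the listed exceptions, some named events are stricter: "When any Grade 3 treatment-related uveitis, pneumonia, bronchospasm, hypersensitivity, or infusion reaction occurs, the study treatment must be terminated". Others are more lenient: endocrine disorders controlled by physiological hormone replacement, and laboratory findings ("The treatment does not need to be terminated for Grade 3 treatment-related laboratory abnormality", with a carve-out for certain thrombocytopenia).

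**The concern.** There are two separate problems.

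The first is inside 6.6.2. A stated stopping rule and the table that is meant to carry it out give different instructions for a Grade 3 event. The rule turns on the word *serious*, which the section does not define.

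The second is between Table 5 and 7.2.4. The Grade 3 row leaves resumption open after discussion, with no limit by event type or duration. It names neither the parties to the discussion nor any criterion that would bring 7.2.4 into it. A site working from the table could re-dose after a Grade 3 pneumonia, or after a Grade 3 colitis that lasted more than 7 days, and 7.2.4 forbids both. Section 16 allows no authorised violation, so the Protocol's own table could lead a site into one.

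Subject safety is what is mainly at stake. A lesser matter is that AEs leading to dose modification or withdrawal are a planned summary (Protocol synopsis), and premature discontinuations are tabulated by reason (SAP 5.2.1). Those counts could partly reflect which text a site followed.

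**Working it through.** No arithmetic applies, and the plan has no figure to reproduce. The check sets the texts side by side for treatment-related Grade 3 events. The second column reads *serious Grade 3* as all Grade 3; the alternative reading follows the table.

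| Grade 3 event | 6.6.2 sentence | Table 5, Grade 3 row | Sections 7.2.2 and 7.2.4 |
|---|---|---|---|
| Uveitis or pneumonia, any duration | Stop | Interrupt, may resume | Must stop |
| Other non-cutaneous, over 7 days, outside the listed exceptions | Stop | Interrupt, may resume | Delay at onset, then must stop |
| Other non-cutaneous, 7 days or less | Stop | Interrupt, may resume | Delay, no mandatory stop |
| Endocrine, controlled by hormone replacement | Stop | Interrupt, may resume | Need not stop |
| Laboratory abnormality below the other 7.2.4 limits | Stop | Interrupt, may resume | Delay in general, need not stop |
| Cutaneous | Stop | Interrupt, may resume | Delay, no Grade 3 stop |

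Infusion reactions are left out because Table 4 and 7.2.4 agree on a permanent stop at Grade 3. In any row, 7.2.4 can also end treatment through the 6-week delay limit or the investigator's judgement of risk.

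**Sentence against Table 5.** Three things favour reading *serious* as a description of Grade 3 itself:

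- Table 4, also within 6.6, labels Grade 3 as serious and Grade 4 as life-threatening, the same two adjectives as the sentence.
- Table 5 uses the parallel pair severe and life-threatening.
- No text separates serious from other Grade 3 immune events.

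If *serious* instead means meeting the SAE definition, the conflict narrows but remains. Table 5 recommends hospitalization at Grade 3, and 9.2.5 says "AEs that result in hospitalization or prolonged hospitalization should be considered as SAEs". A subject hospitalised because of the event therefore falls under the stop in the sentence and under the interruption in the table.

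**Table 5 against 7.2.4.** The first two rows do not depend on the meaning of *serious*. In both, 7.2.4 requires a permanent stop and Table 5 leaves resumption open. For the event over 7 days, interruption is the right first step on either text; the conflict is over what may follow.

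**Sentence against Section 7.** In the last four rows, the sentence read as all Grade 3 stops subjects whom 7.2.2 and 7.2.4 allow to be delayed or continued.

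**Grade 4.** The sentence and the Table 5 Grade 4 row stop permanently without exception. Section 7.2.4 lists exceptions, including endocrine disorders controlled by hormone replacement.

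**The case against.** The strongest defence is that the texts form a hierarchy. Section 6.6 is headed as recommendations, Table 5 is for reference, and 7.2.4 uses mandatory language, so a careful investigator would follow 7.2.4. Read whole, the 6.6.2 sentence makes interruption the default, and *serious* may mark out a subset of Grade 3, with the Table 5 discussion as the place where that subset is identified. Section 7.2.2 sends resumption to 7.2.3. After a hepatic delay, 7.2.3 and 7.3.2 already make resumption depend on the permanent-discontinuation criteria not having been reached. The gastrointestinal and pulmonary algorithms in Annex 4 are not shown, so what a site would read there about colitis or pneumonia cannot be checked.

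Much of this stands. Section 7.2.4 should govern wherever it requires a stop, and 7.3.2 needs no change. But 6.6.2 states no precedence and points to Table 5 and Annex 4, not to 7.2.4. Where 7.2.4 requires no stop, its mandatory wording does not choose between the sentence and the table. The subset reading is possible, but the section supplies no definition for it.

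Three stronger readings are tempting and are not supported:

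- A reader might infer that a Grade 3 liver laboratory abnormality receives three incompatible instructions. It does not. Not having to terminate is compatible with interrupting, and 7.2.2 in general delays dosing for Grade 3 laboratory abnormalities, as Table 5 does. Only the 6.6.2 sentence stands apart.
- A reader might take the table above to show that the sentence and Table 5 disagree for every Grade 3 event. That holds only if *serious* means all Grade 3. The number of rows also depends on how the classes are drawn, so it is not a measure of size.
- A reader might attribute differences in withdrawal rates to this wording. Sections 5.5 and 7.2.4 let investigators stop on their own judgement, so some variation exists by design and no share of it can be assigned.

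**Conclusion.** The point holds as a wording conflict in the current text, in two parts. The 6.6.2 sentence and the Table 5 Grade 3 row conflict: for Grade 3 generally if *serious* describes the grade, and for hospitalised subjects if it means SAE. Table 5, followed as written, also leaves re-dosing open after Grade 3 uveitis or pneumonia, and after other non-cutaneous Grade 3 events over 7 days outside the listed exceptions, where 7.2.4 forbids it. This second part holds on either reading of *serious*.

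The size cannot be given as a rate, because the documents state no frequency for these events. Sample size, endpoints and the primary analysis are unaffected. The conclusion assumes that Table 5 applies to treatment-related immune events of the kinds 7.2.4 names. It relies on nothing in the Annex 4 figures and claims no conflict with the hepatic thresholds in Annex 4. A careful site would reach the right answer through 7.2.4; the risk lies with one that works from 6.6.2 alone. That justifies a correction.

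**What to change.** - **6.6.2 sentence:** replace the trigger (serious Grade 3 or life-threatening Grade 4 events) so that SHR-1210 is discontinued permanently when a criterion in 7.2.4 is met.
- **Table 5, Grade 3 row:** discontinue permanently if any 7.2.4 criterion is met; otherwise delay under 7.2.2 and resume under 7.2.3 after discussion.
- **Table 5, Grade 4 row:** add an exception for the cases listed in 7.2.4.
- **6.6.2:** add one sentence saying that 7.2.2 to 7.2.4 prevail over Table 5 and Annex 4.

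Section 7.3.2 and the thresholds in 7.2.4 and Annex 4 stay as they are. The cost is wording in a protocol amendment and a notice to sites, with no change to sample size, endpoints or analysis.

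### Table 5 (Protocol 6.6.2) leaves a restart open after Grade 3 uveitis or pneumonia, and after Grade 2 ocular events needing systemic therapy, where 7.2.4 requires a permanent stop; the protocol should say that 7.2.4 governs

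*Protocol*

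**What the plan says.** Two parts of the protocol tell a site what to do with SHR-1210 after an immune-related event.

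**Section 6.6.2 and Table 5** work by CTCAE grade alone. The lead-in says that "SHR-1210 should be discontinued permanently when serious Grade 3 or life-threatening Grade 4 adverse events occur". It then tells sites to rely on local practice and guidelines, and introduces the table thus: "The following provides the recommendations on management of immune-related adverse events (see Table 5), for reference". Common events are referred on to Appendix 4.
- Grade 2, clinical treatment: "Local or systemic steroids treatment, 0.5–1 mg/kg/day, Prednisone or equivalent drugs". Action on SHR-1210: "Interrupted temporarily, resume the medication when adverse reactions ≤ Grade 1".
- Grade 3, action on SHR-1210: "Interrupted temporarily; dose resumption must comprehensively consider risk/benefit ratio and be decided after discussion".
- Grade 4: permanent discontinuation, with no exception.

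**Section 7.2.4** is worded as an obligation: "The study medication must be discontinued permanently when the following conditions occur". Its first item is "Any Grade 2 treatment-related uveitis, ophthalmodynia, and blurred vision, that has no response to local therapy and is not recovered to Grade 1" after a dose delay, and it continues "or the above AE requiring systemic therapy". A later item requires termination for any Grade 3 treatment-related uveitis, pneumonia, bronchospasm, hypersensitivity or infusion reaction. For Grade 4 events it lists exceptions, among them endocrine disorders adequately controlled by physiological hormone replacement.

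**The concern.** A site that takes its dosing decision from Table 5 can reach an action that 7.2.4 forbids, and 6.6.2 contains no pointer to 7.2.2, 7.2.3 or 7.2.4 that would correct it. The consequence would be a rechallenge after Grade 3 uveitis or pneumonia, or after a Grade 2 ocular event that needed systemic steroids. That is an avoidable risk to the patient. It is also a protocol violation, in a protocol whose section 16 allows no authorised violations. The sponsor already treats these events as important: section 9.4 lists uveitis and interstitial pneumonia as events of special interest from Grade 2. In the opposite direction, a patient with a hormone-controlled Grade 4 endocrine disorder could lose treatment that 7.2.4 allows to continue.

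**Working it through.** No arithmetic applies. The check sets Table 5 beside 7.2.4, event by event, and then looks for a text that resolves any difference.

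| Event | Table 5 | 7.2.4 | Result |
|---|---|---|---|
| Grade 3 uveitis or pneumonia | Interrupt; restart open after discussion | Terminate | Conflict |
| Grade 2 uveitis, eye pain or blurred vision needing systemic therapy, then recovered to Grade 1 | Resume | Permanent stop | Conflict |
| Grade 2 ocular event, no response to local therapy and not back to Grade 1 after delay | Not resumed, because still above Grade 1 | Permanent stop | No conflict over restart |
| Grade 3 or higher infusion reaction | Handled by Table 4: permanent stop | Grade 3: terminate | Consistent |
| Hormone-controlled Grade 4 endocrine disorder | Permanent stop | May continue | Mismatch, Table 5 stricter |

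**Grade 3.** In 7.2.4 the named events are carved out of the general rule that stops non-cutaneous Grade 3 events lasting more than 7 days. The stop therefore applies whatever the duration. Table 5 makes no exception by type of event, so one text opens a discussion that the other closes.

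**Grade 2.** The need for systemic therapy is a separate trigger in 7.2.4 and is sufficient alone. A Grade 2 uveitis treated with the systemic steroids that Table 5 offers, and recovered, falls under both rules with opposite answers. The exceptions written into the Grade 2 row concern skin and endocrine disorders, not the eye.

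**Does another text settle it?**
- Section 7.2.3 repeats the general rule that dosing can resume at Grade 1 or baseline. It invokes the permanent-stop criteria only in its hepatic item and, for the exceptions, in its 6-week item. A site checking a recovered Grade 2 uveitis against Table 5 and then 7.2.3 gets the same answer twice: resume.
- Section 7.3.2 makes hepatic resumption conditional on no permanent-stop criterion having been reached. Table 5 has no such clause.
- The 6.6.2 lead-in calls for a permanent stop at serious Grade 3, but does not define serious or name events, and the Grade 3 row beneath it leaves restart open.
- Annex 4 cannot be checked in full because its algorithms are figures that are not shown. The pulmonary one may restate the pneumonia stop. The eye appears neither in the systems listed in 7.3.1 nor in the visible Annex 4 headings, so a similar backstop for uveitis is unlikely.

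**The case against.** The strongest reply is that the order of precedence is already legible. Section 6.6 is headed as common recommendations, Table 5 is offered for reference and cites a general position paper, and 7.2.4 is specific and mandatory. A careful reader would follow 7.2.4. The Grade 3 row also does not order a restart: it calls for a discussion, and that discussion is itself bound by 7.2.4. This stands as mitigation and limits the severity. It does not remove the conflict, because 6.6.2 points sites to local practice, guidelines and Appendix 4 rather than to 7.2.4, and 7.2.3 does not catch the Grade 2 case.

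A reader might also infer more than the documents support:
- *That most rows of Table 5 are wrong.* Each row that differs does so only for a narrow set of events, and the Grade 4 difference is in the conservative direction. A count of rows would exaggerate the size.
- *That bronchospasm and hypersensitivity are further conflicts.* Section 6.6.1 treats bronchospasm as a sign of an allergic reaction, and Table 4 already stops such reactions permanently at Grade 3 or above. These largely overlap with Table 4.
- *That failure of local therapy alone triggers the Grade 2 ocular stop.* Section 7.2.4 also requires that the event has not recovered to Grade 1 after the delay, and Table 5 would not resume such a patient either.
- *That Table 5 contradicts the stop after more than 7 days.* It merely omits it; interruption is the right first step under both texts.

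**Conclusion.** The point holds for two situations: Grade 3 treatment-related uveitis or pneumonia, and Grade 2 treatment-related uveitis, eye pain or blurred vision requiring systemic therapy. In both, Table 5 is more permissive than a mandatory rule and no text states which prevails. The Grade 4 mismatch is minor and conservative. The change should be made because the safety gain costs almost nothing; it is not a flaw in the efficacy design, and no effect on ORR or the 6-month OS rate is claimed. The documents give no frequency for these events, so the number of patients affected cannot be estimated.

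The conclusion assumes that the immune-related events handled under Table 5 are treatment-related, since the 7.2.4 items at issue are limited to those, and that pneumonia in 7.2.4 includes immune-mediated lung inflammation. The uveitis part is the firmer one, because the pulmonary figure in Annex 4 is not visible. The asterisk in the Table 5 column heading has no visible note; it may only mark the citation below the table.

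**What to change.** - **Precedence.** State in 6.6.2, and as a note to Table 5, that 7.2.2 to 7.2.4 govern delay, resumption and discontinuation of SHR-1210, and that 7.2.4 overrides both Table 5 and 7.2.3. Ranking 7.2.4 over 7.2.3 is needed because 7.2.3 has the same gap.
- **Lead-in of 6.6.2.** Replace the reference to serious Grade 3 or life-threatening Grade 4 events with *events meeting 7.2.4*.
- **Grade 3 row.** *Interrupt; discontinue permanently if any 7.2.4 criterion is met (including any Grade 3 uveitis or pneumonia); otherwise resume per 7.2.3 after risk/benefit discussion.*
- **Grade 2 row.** Add *unless a 7.2.4 criterion is met (including ocular events requiring systemic therapy)*.
- **Grade 4 row.** Add *except as listed in 7.2.4*.
- **Annex 4.** Check the algorithms against 7.2.4.

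The precedence note also covers the hepatotoxicity stops and the stop after more than 7 days, so the rows need not list them. The cost is protocol wording and a notice to sites, with no change to data collection or analysis.
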